### **9.5. Early Study Termination**

This study can be terminated at any time for any reason by the PI-sponsor. If this occurs, all subjects on study should be notified as soon as possible. Additional procedures and/or follow up should occur in accordance with Section [12.6](#), which describes procedures and process for prematurely withdrawn patients.

## 10. STUDY DRUG

### 10.1. Nivolumab (Opdivo®)

#### 10.1.1. Names, Classification, and Mechanism of Action

Nivolumab is a human monoclonal antibody that blocks the interaction between PD-1 and its ligands, PD-L1 and PD-L2. Nivolumab is an IgG4 kappa immunoglobulin that has a calculated molecular mass of 146 kDa [18].

T-cell proliferation and cytokine production are inhibited by the binding of PD-1 to its ligands, PD-L1 and PD-L2. Some tumors upregulate the PD-1 ligands which contributes to reduced T-cell immune response and surveillance in tumors.

Nivolumab is a human immunoglobulin G4 (IgG4) monoclonal antibody that binds to the PD-1 receptor and blocks its interaction with PD-L1 and PD-L2, releasing PD-1 pathway-mediated inhibition of the immune response, including the anti-tumor immune response. In syngeneic mouse tumor models, blocking PD-1 activity resulted in decreased tumor growth [18].

#### 10.1.2. Packaging and Labeling

Nivolumab is packaged in a clear glass vial with a grey rubber top (100 mg/mL) or a purple rubber top (40 mg/mL).

The label includes the following:

NDC number

“Rx only”

Concentration of solution

“For Intravenous Infusion Only

Single-Dose Vial; Discard Unused Portion”

The label will also include the following statement: “Caution: New Drug—Limited by Federal (or United States) law to investigational use.”

#### 10.1.3. Supply, Receipt, and Storage

Nivolumab is supplied as a clear to opalescent, colorless to pale-yellow solution in a single dose vial of either 100 mg/mL or 40 mg/mL. The vial should be discarded if the solution appears cloudy, is discolored, or contains extraneous particulate matter other than a few translucent-to-white, proteinaceous particles. Nivolumab will be shipped directly from BMS to ICS on ice and should be stored at 2-8°C, protected from heat and light, upon receipt. Do not freeze or shake.

#### 10.1.4. Dispensing and Preparation

Nivolumab is given via IV over 30-60 minutes through an intravenous line containing a sterile, non-pyrogenic, low protein binding in-line filter (pore size of 0.2 micrometer to 1.2 micrometer). The drug product should be visually inspected for particulate matter and discoloration prior to administration and infusion preparation. If the vial of solution appears cloudy, is discolored, or

contains extraneous particulate matter other than a few translucent-to-white, proteinaceous particles, it should be discarded [18]. Do not shake the vial.

The infusion solution should be prepared as follows [18]:

- Withdraw the required volume of nivolumab from the vial and transfer into an intravenous container.
- Dilute nivolumab with either 0.9% Sodium Chloride Injection, USP or 5% Dextrose Injection, USP, to prepare an infusion with a final concentration ranging from 1 mg/mL to 10 mg/mL.
- Mix diluted solution by gentle inversion. Do not shake.
- Discard partially used or empty vials of nivolumab.

The infusion should be administered immediately once prepared. If the diluted nivolumab infusion solution is not used immediately, the solution can be stored at room temperature for up to 4 hours from the time of preparation (including storage of the infusion in the IV container and infusion time) or at 2-8°C for up to 24 hours from the time of preparation [18].

#### **10.1.5. Disposal and Destruction**

All empty vials and used IV bags of nivolumab should be disposed of based on pharmacy guidelines.

### **10.2. Ipilimumab (Yervoy®)**

#### **10.2.1. Names, Classification, and Mechanism of Action**

Ipilimumab is a recombinant, human monoclonal IgG1 kappa immunoglobulin that binds to CTLA-4. CTLA-4 is a negative regulator of T-cell activity.

Ipilimumab binds to CLTA-4 and blocks the interaction with its ligands, CD80/CD86. CTLA-4 blockade has been shown augment the activation and proliferation of tumor-infiltrating T-effector cells. Inhibition of CTLA-4 can also reduce T-regulatory cell function, which may contribute to a general increase in T cell responsiveness, including the anti-tumor response [19].

#### **10.2.2. Packaging and Labeling**

Ipilimumab is packaged in a clear glass vial with a purple rubber top with a red label (200 mg/40 mL) or a teal rubber top with a yellow label (50 mg/ 10mL).

The label includes the following:

NDC number

“Rx only”

Concentration of solution

“For Intravenous Infusion Only

Single-Dose Vial; Discard Unused Portion”

The label will also include the following statement: “Caution: New Drug—Limited by Federal (or United States) law to investigational use.”

### **10.2.3. Supply, Receipt, and Storage**

Ipilimumab is supplied as a clear to slightly opalescent, colorless to pale-yellow solution in a single dose vial of either 50 mg/10 mL or 200 mg/40 mL. The vial should be discarded if the solution appears cloudy, there is pronounced discoloration (solution may have pale-yellow color), or there is foreign particulate matter other than translucent-to-white, amorphous particles. Ipilimumab will be shipped directly from BMS to ICS on ice and should be stored at 2-8°C, protected from heat and light, in the original carton, upon receipt. Do not freeze or shake.

### **10.2.4. Dispensing and Preparation**

Ipilimumab is given via IV over 90 minutes through an intravenous line containing a sterile, non-pyrogenic, low protein binding in-line filter. The drug product should be visually inspected for particulate matter and discoloration prior to administration and infusion preparation. If the vial of solution appears cloudy, is discolored, or contains foreign particulate matter other than a few translucent-to-white, amorphous particles, it should be discarded [19].

The infusion solution should be prepared as follows [19]:

- Allow the vials to stand at room temperature for approximately 5 minutes prior to preparation of infusion.
- Withdraw the required volume of ipilimumab and transfer into an intravenous bag.
- Dilute with 0.9% Sodium Chloride Injection, USP or 5% Dextrose Injection, USP to prepare a diluted solution with a final concentration ranging from 1 mg/mL to 2 mg/mL. Mix diluted solution by gentle inversion.
- Store the diluted solution for no more than 24 hours under refrigeration (2°C to 8°C, 36°F to 46°F) or at room temperature (20°C to 25°C, 68°F to 77°F).
- Discard partially used vials or empty vials of ipilimumab.

The prepared solution should be administered as follows [19]:

- Do not mix ipilimumab with, or administer as an infusion with, other medicinal products.
- Flush the intravenous line with 0.9% Sodium Chloride Injection, USP or 5% Dextrose Injection, USP after each dose.
- Administer diluted solution over 90 minutes through an intravenous line containing a sterile, non-pyrogenic, low-protein-binding in-line filter.

### **10.2.5. Disposal and Destruction**

All empty vials and used IV bags of ipilimumab should be disposed of based on pharmacy guidelines.

## 11. SUBJECT ELIGIBILITY

### 11.1. Inclusion Criteria

1. Patients must have at least 1 previously untreated, solid tumor brain metastasis that is  $\leq 4$  cm in the largest dimension that is planned for standard of care surgical resection. Metastasis must be planned for treatment with post-surgical SRS per standard of care. Primary tumor histology must be one of the following:
  - Squamous NSCLC
  - Non-squamous NSCLC without known ALK, EGFR, and ROS mutation
  - RCC
  - Urothelial carcinoma
  - Ovarian carcinoma
  - Melanoma
  - Triple negative breast cancer that is PD-L1 positive
  - Other solid tumor histologies may be eligible at the discretion of the PI if they are known to respond to immunotherapy containing regimens.
2. Patient must be asymptomatic or minimally symptomatic, requiring the equivalent of  $\leq 4$  mg dexamethasone daily for at least 7 days prior to enrollment
3. Patient or partner(s) meets one of the following criteria:
  - a) Non-childbearing potential (i.e. not sexually active, physiologically incapable of becoming pregnant, including any female who is post-menopausal or surgically sterile, or any male who has had a vasectomy). Surgically sterile females are defined as those with a documented hysterectomy and/or bilateral oophorectomy or tubal ligation. Postmenopausal for purposes of this study is defined as 1 year without menses.; or
  - b) Childbearing potential and agrees to use one of the following methods of birth control: approved hormonal contraceptives (e.g. birth control pills, patches, implants, or infusions), an intrauterine device, or a barrier method of contraception (e.g. a condom or diaphragm) used with spermicide.
4. Age  $\geq 18$  years of age at the time of entry into the study
5. Karnofsky Performance Score (KPS)  $\geq 70$
6. Prothrombin and Partial Thromboplastin Times  $\leq 1.2 \times$  normal at screening
7. Neutrophil count  $\geq 1000$  at screening
8. Hemoglobin  $\geq 9$  g/dl at screening
9. Platelet count  $\geq 100,000/\mu\text{l}$  unsupported is necessary at screening
10. Creatinine  $\leq 1.5 \times$  ULN at screening
11. A signed informed consent form approved by the Institutional Review Board (IRB) will be required for patient enrollment into the study. Patients must be able to read and understand the informed consent document and must sign the informed consent indicating that they are aware of the investigational nature of this study
12. Ability to undergo MRI

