## 12. SCREENING AND ON-STUDY TESTS AND PROCEDURES

**Table 1: Schedule of Study Tests and Procedures**

Description	Screening	Treatment Period				
	Up to 14 days prior to surgical resection	Neoadjuvant IO	Surgery		Adjuvant SRS 	Follow-up
Week 		-1	1	3 	4	7, 13 +SOC visits
Day 		-10 to -4	1	15	22 ( $\pm$ 3 weeks)	29 + SOC visits
General Evaluations						
Informed Consent	X					
Physical Exam 	X	X	X	X		X
Neurologic Exam 	X	X	X	X		X
Performance Status 	X	X	X	X		X
Adverse Events					Continuous 	
Laboratory Evaluations						
CBC w/diff	X	X 	X	X		X
CMP	X	X 	X	X		X
Thyroid panel	X					X
PT, aPTT	X					
Pregnancy test 	X	X 				
Whole blood for correlative analysis (3x10 mL yellow top) 	X		X 	X	X 	X 
Archival tissue sample 	X					
Surgical tissue sample			X 			
Disease Evaluations						
MRI of the brain 	X					X 
Treatment						
Ipilimumab		X				
Nivolumab		X				
Surgery 			X			
SRS					X	

Number of fractions for SRS treatment will be assigned at physician's discretion

Weeks and days listed are approximate.

Post-operative visit

Clinical evaluations will include a general physical examination, complete neurologic examination, and KPS rating.

Adverse events will be continuously monitored after the first study-mandated agent is administered to the patient and reviewed monthly by the study PI. AE collection will cease 100-days after surgery, or 100 days after ipilimumab/nivolumab infusion for patients who do not undergo surgery.

Only drawn if more than 7-days (24-hours for pregnancy) post screening draw

For women of childbearing potential

Whole blood should be sent to the Substrate Services Core (SSCRS) for processing and then sent to [name] laboratory

Blood should be drawn prior to surgical resection

Blood should be drawn prior to SRS

Drawn only at the week 7 follow-up visit

A sample of archival tissue from the primary or other extracranial tumor will be requested for correlative analysis, if available.

A sample of tissue from the resected metastases will be requested for correlative analysis, if available.

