## 12.1. Screening Examination

All screening procedures should occur within 14 days prior to the planned surgical resection. An informed consent form must be signed by the patient prior to initiating any screening tests or procedures. Screening test and procedures include a physical exam, neurological exam, performance (KPS) status, a pregnancy test, and blood tests. Blood for immune monitoring will also be collected during screening. An archival tissue sample from the primary tumor will be requested for correlative analysis, if available.

If a subject does not receive nivolumab or ipilimumab, minimal records regarding the subject will be retained in the study database. Participants who screen fail after providing informed consent but before receiving study-related treatment will be withdrawn, and these subjects will be excluded from all analyses.

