## 12.2. Treatment Period

### Day -10 to -4:

- Physical exam, neurological exam, and KPS
- Laboratory testing including:
  - CBC with differential
  - CMP
  - Beta-HCG, if appropriate and > 24 hours post screening Beta-HCG
- Ipilimumab infusion
- Nivolumab infusion

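### Inclusion 3a counts reported abstinence as non-childbearing potential, so a fertile woman can enter without the 3b contraception agreement and her repeat pregnancy test before infusion is not clearly required

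*Combined protocol and SAP*

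**What the plan says.** Inclusion 3 in Section 11.1 offers a choice: "Patient or partner(s) meets one of the following criteria". The first option begins "Non-childbearing potential (i.e. not sexually active, physiologically incapable of becoming pregnant" and then names postmenopausal or surgically sterile females and vasectomised males. Sterility is defined there, and so is menopause: "Postmenopausal for purposes of this study is defined as 1 year without menses". No duration or continuation is attached to sexual inactivity. The second option is the only one with an undertaking: "Childbearing potential and agrees to use one of the following methods of birth control". Abstinence is not among the methods it lists.

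Table 1 marks the pregnancy test at two time points, screening and the infusion visit (Day -10 to -4). Footnote 7 restricts the row: "For women of childbearing potential". Footnote 6 governs the second time point: "Only drawn if more than 7-days (24-hours for pregnancy) post screening draw".

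The text sections are worded differently. Section 12.1 sets no restriction: "Screening test and procedures include a physical exam, neurological exam, performance (KPS) status, a pregnancy test, and blood tests". Section 12.2, for the infusion visit, says "Beta-HCG, if appropriate and > 24 hours post screening Beta-HCG". Section 12.7.4 lists the test with the same qualifier, 'if appropriate'.

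Section 9.1.3 warns that nivolumab can harm a fetus and advises females of reproductive potential to use effective contraception until at least 5 months after the last dose. Exclusion 1 in Section 11.2 bars pregnant or breast-feeding females.

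**The concern.** Menopause and sterility are physiological states. Sexual inactivity is a behaviour that is self-reported and can change. By placing it beside the other two, 3a gives a fertile woman the same label as a woman who cannot conceive, and that label relieves her of the only undertaking in the criterion.

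The label may also carry over into testing, because footnote 7 uses closely related wording and the protocol has no separate definition of who is tested. Each drug is given once (9.1.4). A test before that infusion is therefore the only scheduled test that can show an existing pregnancy in time to prevent exposure. The later provisions on pregnancy act once it is known: withdrawal in 12.6.1, handling as a serious adverse event in 13.2, and reporting in 13.2.1. What is at stake is the safety of a small number of patients, not the analysis.

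**Working it through.** There is no plan figure to reproduce; this is a comparison of provisions.

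1. **How 3a parses.** The comma after 'not sexually active' could mean that both conditions must hold, or that each suffices. The list ends with vasectomised males as a further alternative, and there is no reason to require a sterile or postmenopausal woman to be abstinent as well. A list of alternatives is the natural reading.

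2. **Contraception.** Because 3a or 3b suffices and only 3b contains the agreement, a premenopausal, non-sterile woman who reports abstinence qualifies under 3a with nothing agreed.

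3. **Testing.** For the same woman:

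| Provision | Screening test | Repeat before infusion |
|---|---|---|
| Footnote 7, read through 3a | not required | not required |
| Footnote 7, ordinary meaning | required | required if more than 24 hours have passed |
| Section 12.1 alone | listed, no restriction | not addressed |
| Section 12.2 alone | not addressed | only if judged appropriate |

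Footnote 7 thus gives 0 of 2 tests or 2 of 2, depending on the reading. Section 12.1 supports the first test only.

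4. **Why the repeat matters.** Screening may take place up to 14 days before surgery, and the infusion 10 to 4 days before it. The gap between them can reach 14 − 4 = 10 days, well beyond the 24 hours in footnote 6. The screening test in 12.1 therefore does not stand in for the repeat.

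5. **How many patients.** The documents give no figure for the share of such women. As an assumption only, take a share p of 1%, 5% or 10% among 20 patients:
 - expected number = 20p = 0.2, 1 or 2;
 - chance of enrolling at least one = 1 − (1 − p)^20 = 1 − 0.818 = 18%, 1 − 0.358 = 64%, or 1 − 0.122 = 88%.

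These are chances that such a woman enrols. They say nothing about the chance of fetal exposure.

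**The case against.** The testing gap exists only if 3a is carried into footnote 7. The footnote does not refer to 3a, and 3a does not define women of childbearing potential. It describes non-childbearing potential, for an item that covers patients and partners of either sex. In ordinary usage a premenopausal, non-sterile woman has childbearing potential and would be tested twice. Section 12.1 also lists a screening test for everyone, exclusion 1 bars a pregnant woman however she was classed under inclusion 3, and 'if appropriate' leaves the investigator free to test her. All of this stands. A reader might infer that the protocol exempts her from testing or tells sites to skip the test; no provision says so. What remains is that the provisions disagree about her screening test and none clearly requires the repeat.

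On contraception, a woman who stays abstinent has no conception risk for 3b to control, and the advice in 9.1.3 already covers her. That reduces the weight of the point but does not remove it: 3a asks for no commitment to stay abstinent, and the advice in 9.1.3 is a recommendation in a safety narrative, not a condition of entry.

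The consent pages are not in the text available for this review. They may contain an undertaking on pregnancy or contraception, and this cannot be judged.

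**Conclusion.** The eligibility part follows from the wording: a fertile woman who reports abstinence enters without the 3b agreement and without committing to continued abstinence. The testing part is an inconsistency, not an omission. Her screening test depends on which provision a site follows, and her repeat before infusion depends on how footnote 7 and 'if appropriate' are read.

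The practical size is small. For exposure at dosing, she would have to be pregnant despite reporting abstinence, the site would have to read footnote 7 through 3a and not act on 12.1, and exclusion 1 would have to fail to identify her. A reader might take the enrolment chances under the assumed shares as a risk of fetal harm; the documents support no such figure. The absence of any scheduled test after infusion applies to every patient and is not evidence for this point. Neither primary endpoint is affected. The change is still worth making, because the protocol itself warns of fetal harm and the correction is cheap. Confidence is moderate, since part of the point rests on how a site reads a footnote and the consent pages were not available.

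**What to change.** - **3a:** delete 'not sexually active'.
- **3b:** add continued abstinence as an accepted method, so that abstinent patients need not agree to hormones, a device or a barrier. For female patients, state that it holds for at least 5 months after the dose, to match 9.1.3.
- **Table 1, footnote 7:** define the tested group as every female who is neither postmenopausal nor surgically sterile as 3a defines these.
- **12.2 and 12.7.4:** replace 'if appropriate' with that group, keeping the 24-hour rule for the repeat.
- **12.1:** leave as it is, or add a reference to footnote 7.

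The cost is one wording amendment, at most two routine pregnancy tests per affected woman at visits that already list laboratory work, and a recorded abstinence agreement from patients who would now enter under 3a as sexually inactive. Visit timing, sample size and analysis do not change.

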### **9.1.2. Dose Modification**

#### **9.1.2.1. Non-hematologic:**

Not applicable, only one dose of the study drug is given so there will be no intra-patient dose reduction. Similarly, the proposed doses of 3 mg/kg for nivolumab and 1 mg/kg for ipilimumab are recommended by the FDA.

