Grade 2-3 Mild to moderate new symptoms	
 
Delay I-O therapy per protocol
 
Pulmonary and ID consults
 
Monitor symptoms daily, consider hospitalization
 
1.0 mg/kg/day methylprednisolone IV or oral equivalent
 
Consider bronchoscopy, lung biopsy
 
	
 
Re-image every 1-3 days
 
 
If improves:
 
 
When symptoms return to near baseline, taper steroids over at least 1 month and then resume I-O therapy per protocol and consider prophylactic antibiotics
 
 
If not improving after 2 weeks or worsening:
 
 
Treat as Grade 3-4
 

Grade 4 Severe new symptoms; New/worsening hypoxia; Life-threatening	
 
Discontinue I-O therapy per protocol
 
Hospitalize
 
Pulmonary and ID consults
 
2-4 mg/kg/day methylprednisolone IV or IV equivalent
 
Add prophylactic antibiotics for opportunistic infections
 
Consider bronchoscopy, lung biopsy
 
	
If improves to baseline:
 
 
Taper steroids over at least 6 weeks
 
 
If not improving after 48 hours or worsening:
 
 
Add additional immunosuppression
 

Patients on IV steroids may be switched to an equivalent dose of oral corticosteroids (e.g. prednisone) at start of tapering or earlier, once sustained clinical improvement is observed. Lower bioavailability of oral corticosteroids should be taken into account when switching to the equivalent dose of oral corticosteroids.

**Table 5: Hepatic Adverse Event Management Algorithm.** Rule out non-inflammatory causes. If non-inflammatory cause, treat accordingly and continue I-O therapy. Consider imaging for obstruction.

Grade of Liver Test Elevation	Management	Follow-up
Grade 1 AST or ALT > ULN to 3.0 x ULN and/or T. bili > ULN to 1.5 x ULN	
 
Continue I-O therapy per protocol
 
	
 
Continue LFT monitoring per protocol
 
 
If worsens:
 
 
Treat as Grade 2 or 3-4
 

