Grade 2 AST or ALT > 3.0 to ≤ 5 x ULN and/or T. bili > 1.5 to ≤ 3 x ULN	
 
Delay I-O therapy per protocol
 
Increase frequency of monitoring to every 3 days
 
	
If returns to baseline:
 
 
Resume routine monitoring, resume I-O therapy per protocol
 
 
If elevation persists > 5-7 days or worsens:
 
 
0.5-1 mg/kg/day methylprednisolone or oral equivalent and when LFT returns to grade 1 or baseline, taper steroids over at least 1 month, consider prophylactic antibiotics for opportunistic infections, and resume I-O therapy per protocol
 

Grade 3-4 AST or ALT > 5 x ULT or T. bili > 3 x ULN	
 
Discontinue I-O therapy per protocol*
 
Increase frequency of monitoring to every 1-2 days
 
1.0 to 2.0 mg/kg/day methylprednisolone IV or IV equivalent*
 
Add prophylactic antibiotics for opportunistic infections
 
Consult gastroenterologist
 
	
If returns to Grade 2:
 
 
Taper steroids over at least 1 month
 
 
If does not improve in >3-5 days, worsens or rebounds:
 
 
Add mycophenolate mofetil 1 g BID
 
If no response within an additional 3-5 days, consider other immunosuppressants per local guidelines
 

Patients on IV steroids may be switched to an equivalent dose of oral corticosteroids (e.g. prednisone) at start of tapering or earlier, once sustained clinical improvement is observed. Lower bioavailability of oral corticosteroids should be taken into account when switching to the equivalent dose of oral corticosteroids.

\*The recommended starting dose for grade 4 hepatitis is 2 mg/kg/day methylprednisolone IV.

**Table 6: Endocrinopathy Adverse Event Management Algorithm.** Rule out non-inflammatory causes. If non-inflammatory cause, treat accordingly and continue I-O therapy. Consider visual field testing, endocrinology consultation, and imaging.

Asymptomatic TSH Elevation	
 
Continue I-O therapy per protocol
 
If TSH < 0.5 x LLN, or TSH > 2 x ULN, or consistently out of range in 2 subsequent measurements: include fT4 at subsequent cycles as clinically indicated; consider endocrinology consult
 
	

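### No AST, ALT or bilirubin limit governs entry or the single nivolumab/ipilimumab infusion, so a patient with unexplained raised liver tests is eligible as written

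*Combined protocol and SAP*

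**What the plan says.** **Eligibility.** Section 11.1, items 6 to 10, holds the laboratory limits: "Prothrombin and Partial Thromboplastin Times" (no more than 1.2 x normal), neutrophils, hemoglobin, platelets, and creatinine (no more than 1.5 x ULN). No liver enzyme or bilirubin limit appears there, and 11.2 names no liver test.

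**Infusion visit.** Section 12.2 (Day -10 to -4) lists a CBC, a CMP and, where relevant, a pregnancy test, followed by "Ipilimumab infusion" and the nivolumab infusion. Table 1 footnote 6 repeats the CMP only when the screening draw is more than 7 days old. Neither place attaches a consequence to a liver result.

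**Dose modification.** Section 9.1.2.1 reads "Not applicable, only one dose of the study drug is given so there will be no intra-patient dose reduction".

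**Where liver values do appear.** They are in the adverse-event algorithms of the appendix. Table 5 (nivolumab) sets its Grade 2 range as "AST or ALT > 3.0 to ≤ 5 x ULN and/or T. bili > 1.5 to ≤ 3 x ULN", with the action "Delay I-O therapy per protocol", and its Grade 3-4 range as "AST or ALT > 5 x ULT or T. bili > 3 x ULN" (the ULT is read here as ULN), with the action to discontinue. Table 11 (ipilimumab) has the same structure with a lower AST/ALT delay point.

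**The concern.** Each drug is given once. The hepatic algorithms act on the drug mainly by continuing, delaying or stopping it, and after the infusion no study dose is left to delay or stop. The decision to infuse is the only moment at which a hepatic hold rule could protect the patient. CMPs on Day 1, at Weeks 3, 7 and 13 and at later standard-of-care visits, and the handling of potential drug-induced liver injury as an SAE (13.2), can detect harm but cannot take the dose back.

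The protocol treats the liver as an organ at risk: 9.1.3 lists liver inflammation among rare but potentially serious nivolumab effects, and each drug has its own hepatic table. It sets entry rules for kidney (creatinine) and lung (11.2 item 10), but none for AST, ALT or bilirubin, and does not say why. What is at stake is patient safety.

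**Working it through.** No sample-size or power figure is involved, so the check sets the sections side by side.

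**Step 1: is there a limit anywhere before dosing?**
- 11.1: 12 inclusion criteria, 0 with an AST, ALT or bilirubin value.
- 11.2: 10 exclusion criteria, 0 with such a value. Item 3c (unstable or severe intercurrent illness) gives a cardiac example only. Item 4 (unrecovered toxicity of earlier chemotherapy or radiation) carries no grade or value.
- 12.2, and Table 1 with its footnotes: 0 liver values that withhold the infusion.
- 9.1.2: no hold rule.
- 12.6.1: the investigator may withdraw a patient, by judgment.

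**Step 2: what do the algorithms do at each level?**

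| Result (x ULN) | 11.1 / 11.2 | Table 5, nivolumab | Table 11, ipilimumab |
|---|---|---|---|
| AST/ALT > 2.5 to 3.0 | eligible | continue | withhold/delay |
| AST/ALT > 3.0 to 5 | eligible | delay | withhold/delay |
| AST/ALT > 5 | eligible | discontinue | discontinue (may be held if AST/ALT <= 8 and bilirubin < 5) |
| Bilirubin > 1.5 to 3 | eligible | delay | withhold/delay |
| Bilirubin > 3 | eligible | discontinue | discontinue (same exception) |

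The continue entry in the first row is Table 5 Grade 1: "AST or ALT > ULN to 3.0 x ULN and/or T. bili > ULN to 1.5 x ULN". Both tables make an exception; Table 5 puts it as "If non-inflammatory cause, treat accordingly and continue I-O therapy. Consider imaging for obstruction". The delay and discontinue entries therefore describe elevations without a non-inflammatory explanation.

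Example: an unexplained AST of 6 x ULN at screening breaks no numeric entry rule. Table 5 would discontinue at that value. Table 11 would discontinue or, under its footnote, hold.

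**Step 3: do the tables already apply before the dose?** The text points both ways.
- For: 13.1 records AEs from consent, counts CTCAE-gradable laboratory findings and refers to 18.1 and 18.2. Table 11 Grade 1 mentions liver-test monitoring ahead of each dose.
- Against: 13.1 defines an AE as arising in someone receiving study drug. Table 1 footnote 5 starts monitoring after the first agent. The Table 5 delay action refers back to the protocol, whose dose-modification section contains no hold rule.

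The tables therefore do not clearly supply the missing criterion.

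**Step 4: limits consistent with the tables.** The stricter delay point for two drugs given at the same visit is min(3.0, 2.5) = 2.5 x ULN for AST/ALT and min(1.5, 1.5) = 1.5 x ULN for bilirubin. The point where both tables generally discontinue is 5 x ULN for AST/ALT and 3 x ULN for bilirubin.

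**The case against.** The strongest reply is that the protocol relies on judgment and that judgment will usually be enough. A CMP is drawn at screening and repeated if stale. Exclusions 3c and 4, KPS of at least 70 and the coagulation limit keep out some patients with serious liver dysfunction. The investigator may withdraw anyone, and one PI-sponsor reviews AE attribution, so inconsistent decisions between investigators are a weak argument. This stands in part: grossly abnormal results are unlikely to be ignored. But none of these safeguards carries an AST, ALT or bilirubin value, and coagulation times reflect liver function only partly.

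The second reply is that the thresholds come from tables written for toxicity management. That also stands in part. A reader might infer that dosing any patient above the Table 5 or Table 11 delay points contradicts the protocol. It does not: with a non-inflammatory cause, both tables continue therapy and set no ceiling. The point is confined to unexplained elevations.

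Third, a reader might take 9.1.2 to mean that the dose cannot be withheld. It rules out dose reduction only; 12.6.1 and 12.6.3 foresee patients who are never infused. The difficulty is that no section says when to withhold.

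**Conclusion.** The point holds and should be acted on. As written, no upper limit on AST, ALT or bilirubin applies at entry or at any of the up to 20 infusion decisions, so an unexplained result in the delay or discontinue range of the protocol's own tables does not bar the dose.

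Its size cannot be given as a number of patients or a probability. The documents state neither how often screening liver tests are abnormal nor how much risk a raised baseline adds. A reader might infer a measurable excess of hepatic events, or bias in the surgical-delay endpoint; the documents support neither, and neither is claimed. Dividing the tables' discontinue points by the limits proposed here would measure only the proposal, not the trial.

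The conclusion rests on two readings: that the hepatic tables do not clearly govern the pre-dose decision, and that the discretionary safeguards set no hepatic threshold.

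**What to change.** Add to 11.1: *AST and ALT <= 2.5 x ULN and total bilirubin <= 1.5 x ULN at screening; AST/ALT <= 5 x ULN and total bilirubin <= 3 x ULN are allowed if due to documented liver metastases or another documented non-inflammatory cause (e.g. a benign bilirubin elevation).*

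Add to 12.2: *The most recent CMP before infusion (the screening draw if no more than 7 days old, otherwise the repeat) must meet this limit, or neither drug is given.*

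The general limits are the stricter delay points from the two tables. The upper caps are where both tables generally discontinue. For non-inflammatory causes the tables set no cap, so those caps are a proposal for the investigators to confirm. The 2.5 x ULN limit also withholds nivolumab for unexplained AST/ALT between 2.5 and 3.0 x ULN, where Table 5 alone would continue; this follows from giving both drugs at one visit.

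Cost: two additions in an amendment. No new test is needed, assuming the CMP includes AST, ALT and bilirubin (12.7.4 does not list its components). Possibly a few fewer patients will be eligible. Section 15.1 reports enrollment difficulty but attributes it to the control arm, since removed. A patient stopped before receiving both drugs is replaced under 12.6.3, so the target of up to 20 treated patients need not change.
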